3.3 Research Content

3.3.1 Stratification, Blinding, and Intervention

After stratifying subjects according to the Cleveland Clinic scoring system for predicted dialysis-required AKI risk (high risk: ≥ 6 points vs. low-to-moderate risk: 1-5 points), independent statisticians generated computer-generated block random sequences (block size: 2 or 4) to assign participants at a 1:1 ratio to either the ta-VNS group or sham stimulation group. The grouping results were sealed in sequentially numbered opaque envelopes.

Blinding was implemented for both participants and outcome evaluators. After obtaining informed consent from participants, a non-blind study coordinator who would not be involved in subsequent clinical work publicly opened the envelope, recorded the grouping information, and handed it to a trained non-blind operator to execute the corresponding stimulation protocol. Other researchers (including those responsible for follow-up, data collection, testing, and statistical analysis) remained unaware of the grouping assignments.

The ta-VNS group received electrical stimulation via a transcutaneous auricular vagus nerve stimulator (tVNS501) applied to the left auricular cartilage. The parameters were set as follows: frequency 25Hz, pulse width 250 μ s, with a stimulation-interval cycle of 30 seconds stimulation followed by 30 seconds rest. The stimulation intensity was incrementally increased starting from 0.4V in 0.4V increments until the subject experienced pain, then adjusted downward to just below the pain threshold to determine the optimal stimulation intensity. The stimulation coverage spanned preoperative, intraoperative, and postoperative phases: beginning on the day of surgery upon entering the preoperative preparation room and continuing until the patient was transferred to the ICU, followed by 6 hours of stimulation. From postoperative days 1 to 5, the stimulation regimen was restored to twice daily (at 9:00 AM and 2:00 PM) with each session lasting 120 minutes [42-44].

In the sham-stimulation group, electrodes were placed at the same site and within the same cycle period with optimal intensity determined, but stimulation output was turned off without administering actual electrical stimulation.

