3.3.2.3 Basic Clinical Indicators

Prior to randomization of patients, trained investigators collected the following baseline data. All measurements were based on the most recent test conducted after hospital admission and prior to surgery, and must be completed before randomization.

Demography and anthropometry: age, gender, height, weight, body mass index (BMI), ASA classification.

Cardiac function and risk scoring: NYHA cardiac function classification, left ventricular ejection fraction, EuroSCORE II score, Cleveland Clinic score, history of cardiac surgery, recent myocardial infarction (MI) history (<3 months).

Clinical history and comorbidities: history of hypertension, diabetes mellitus, chronic kidney disease, cerebrovascular disease, peripheral vascular disease, chronic obstructive pulmonary disease, hepatic insufficiency (Child-Pugh classification), smoking history, and alcohol consumption history.

Preoperative medication history: Record medications used within 24 hours prior to randomization that cannot be safely discontinued, including RAS inhibitors, β -blockers, calcium channel blockers, diuretics, statins, antiplatelet agents, oral hypoglycemic agents or insulin, and nonsteroidal anti-inflammatory drugs (within 48 hours before surgery).

Baseline laboratory tests: serum creatinine, eGFR (CKD-EPI formula), blood urea nitrogen, hemoglobin, platelet count, albumin, myocardial troponin I, NT-proBNP, and high-sensitivity C-reactive protein.

Surgical parameters: Type of surgery, surgical urgency, extracorporeal circulation time, aortic cross-clamping duration, minimum nasopharyngeal temperature, intraoperative red blood cell transfusion volume, intraoperative urine output, and use of vasoactive drugs during surgery.

Previous intervention history: Whether the participant received vagus nerve stimulation, auricular acupuncture, transcutaneous electrical stimulation therapy, or participated in other clinical studies within 1 month prior to enrollment.

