GEE were employed to analyze differences in the temporal variation trajectories of routine laboratory parameters and plasma IL-6/NGAL levels between two groups. The model included grouping, time, and their interaction as fixed effects, with subjects as random effects. Appropriate work-related matrices and distribution families were selected to assess the significance of the group \times time interaction. Independent samples t-test or Mann-Whitney U test was used to compare postoperative monocyte α 7nAChR expression levels, intracellular IL-6+ proportion, and Th17/Treg ratio at various time points between the two groups. GEE analysis was also conducted to evaluate overall trends and intergroup differences. Spearman correlation analysis was employed to investigate associations between immune cell markers (α 7nAChR, IL-6+, Th17/Treg), plasma biomarkers (IL-6, NGAL), and clinical outcomes (AKI incidence rate, peak serum creatinine level).

[figure not shown]
To determine the minimum number of stimulation days required to achieve clinical efficacy, the completion of stimulation was defined as when the actual daily stimulation duration reached $\geq 80\%$ of the planned duration. Based on the total number of days (0-6 days) during which subjects completed stimulation, a multivariate logistic regression analysis was performed to examine the dose-response relationship between cumulative stimulation days and the incidence of AKI, thereby identifying the critical number of days when the protective effect tends to plateau.

Subgroup analysis was conducted based on the following prespecified factors: gender, left ventricular ejection fraction (<35% vs. $\geq 35\%$), age (<65 years vs. ≥ 65 years), preoperative eGFR (<90 vs. ≥ 90 mL/min/1.73 m²), CPB duration (<120 min vs. ≥ 120 min), and surgical type (high-risk group [valve and coronary artery combined/aortic surgery] vs. low-to-moderate risk group [valve and septal repair]). Subgroup analysis was implemented in single-factor logistic regression models by introducing interaction terms between grouping and subgroup variables, with OR values and 95% CI for each subgroup visually presented in forest plots.

Safety analysis was based on the safety dataset (all subjects who received at least one stimulation). The incidence rates of all adverse events and serious adverse events were compared between groups using the χ^2 test or Fisher's exact probability method.

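### CPB duration is prespecified as a subgroup factor and listed as pre-randomisation data, but it arises after stimulation starts; the subgroup result may be biased if stimulation or knowledge of allocation affects it

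*Combined protocol and SAP*

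**What the plan says.** Section 3.3.3 names six prespecified subgroup factors. Five are gender, ejection fraction, age, preoperative eGFR and surgical type; the other is "CPB duration (<120 min vs. ≥ 120 min". All six get the same analysis: a logistic model "introducing interaction terms between grouping and subgroup variables", with the odds ratio for each subgroup shown in a forest plot. Nothing marks CPB duration as different in kind.

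Section 3.3.2.3 opens with "Prior to randomization of patients, trained investigators collected the following baseline data" and then sets the rule: "All measurements were based on the most recent test conducted after hospital admission and prior to surgery, and must be completed before randomization". The list under that rule includes "Surgical parameters: Type of surgery, surgical urgency, extracorporeal circulation time, aortic cross-clamping duration", followed by minimum temperature and intraoperative transfusion, urine output and vasoactive drugs. Extracorporeal circulation time is CPB duration under another name.

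Section 3.3.1 describes stimulation as "beginning on the day of surgery upon entering the preoperative preparation room and continuing until the patient was transferred to the ICU", with further sessions after that. Section I (Research Background) states that the risk of CPB-associated AKI is positively correlated with CPB duration.

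**The concern.** A subgroup comparison keeps the protection of randomisation when the factor is fixed before allocation. CPB duration is not: it is known only when bypass ends, after randomisation and with stimulation already running. If the intervention, or someone's knowledge of the allocation, moves patients across the 120-minute cut, the short-CPB patients in one arm are no longer the same kind of patient as those in the other. Because CPB duration is prognostic for AKI, the odds ratios within the two strata can then differ from the true effect, and so can the interaction.

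Two features of the plan make this easy to miss. The factor sits beside true baseline factors and shares their forest plot, so a reader would take its row as randomised evidence. The data list also labels it as pre-randomisation, so the report could describe it as baseline.

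**Working it through.** **Timing.** Set side by side, the sections give this order:

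1. Section 3.3.2.3: the listed data are complete before randomisation.
2. Section 3.3.1: stimulation begins in the preparation room on the day of surgery.
3. Surgery and bypass follow while stimulation continues; CPB duration becomes known when bypass ends.
4. Section 3.3.3: CPB duration defines a subgroup.

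Step 1 cannot be met for CPB time, cross-clamp time, minimum temperature or the intraoperative transfusion, urine output and vasoactive drug items. No section substitutes a planned or predicted CPB duration, and none labels this subgroup as post-randomisation.

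**Size of a possible bias.** The plan gives no figure on this point, so what follows is an illustration. Assumed inputs, none from the documents:

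- Half of sham patients have CPB of 120 minutes or more.
- Stimulation has no effect on AKI in any patient.
- Stimulation moves a share m of all patients in its arm from the long to the short stratum.
- AKI risks for always-short, shifted and always-long patients (rs, rm, rl) are 30/45/45% in scenario A and 25/40/50% in scenario B. Overall risk is 37.5% in A and 36.0 to 37.5% in B, close to the 37.9% sham rate in section IV.

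Formulas:

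- Short stratum: sham risk = rs; ta-VNS risk = (0.5·rs + m·rm)/(0.5 + m).
- Long stratum: sham risk = [m·rm + (0.5 − m)·rl]/0.5; ta-VNS risk = rl.

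Worked case, scenario B with m = 10%:

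- Short: (0.125 + 0.040)/0.60 = 27.5% against 25.0%; odds 0.379 against 0.333; OR 1.14.
- Long: 50.0% against (0.040 + 0.200)/0.50 = 48.0%; odds 1.000 against 0.923; OR 1.08.

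| m | A: short OR | A: long OR | B: short OR | B: long OR |
|---|---|---|---|---|
| 0% | 1.00 | 1.00 | 1.00 | 1.00 |
| 5% | 1.07 | 1.00 | 1.07 | 1.04 |
| 10% | 1.12 | 1.00 | 1.14 | 1.08 |
| 15% | 1.17 | 1.00 | 1.19 | 1.13 |

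The true OR is 1.00 in every cell. Swapping the arms, so that stimulation lengthens bypass, gives the reciprocals.

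**Scale against sampling error.** Section IV gives 76 patients per group (68/0.9 = 75.6, rounded up) and AKI rates of 17.1% and 37.9%. With an even split there are 38 patients per cell. If both strata have those rates, the standard error of the log ratio of odds ratios is

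√{2 × [1/(38 × 0.171 × 0.829) + 1/(38 × 0.379 × 0.621)]} = √(2 × 0.2974) = 0.771.

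The ratio detectable with 80% power at two-sided 0.05 is exp[(1.960 + 0.842) × 0.771], about 8.7. The largest distortion of the interaction in the table is scenario A at m = 15%: a long-to-short ratio of 1.00/1.173 = 0.85. On the log scale that is 0.16, about a fifth of one standard error.

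**The case against.** The strongest reply is that the harm is conditional and small. Bias needs CPB duration to be changed by stimulation or by knowledge of allocation, and the documents neither show nor exclude this. A route can be inferred: section I expects vagal stimulation to improve circulatory function, and section 3.3.1 does not name surgeons, anaesthetists or perfusionists among those blinded. An inferred route is not evidence of an effect. The illustrated distortion also rests on assumed inputs and is lost in the sampling error. All of this stands, and it limits the point.

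It can also be said that section 3.3.3 calls the factors prespecified, not baseline, and that the entry in section 3.3.2.3 is a slip of placement that nobody could carry out literally. That is fair. Even so, the plan gives CPB duration the same footing as baseline factors, and nothing in the text corrects the slip.

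A reader might infer three stronger things that the documents do not support:

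- That an interaction with CPB duration can never be read as effect modification. If duration is unaffected by allocation, the subgroup comparison is unbiased.
- That the result is useless for deciding on treatment because CPB time is unknown at that point. This holds for the start of stimulation only; the postoperative sessions come after CPB time is known, and the plan does not propose selecting patients by it.
- That surgical type already covers the question. Duration can vary within a surgical type, so it is a proxy and not an equivalent.

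**Conclusion.** The point holds in conditional form. CPB duration is a post-randomisation variable that the plan places on the footing of a baseline factor, and the data-collection rule for it cannot be met. The subgroup odds ratios and interaction may be biased if stimulation or knowledge of allocation affects CPB duration, and are not biased by this route otherwise.

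The size cannot be derived from the documents. Under the stated assumptions, with no true effect, the short-CPB odds ratio is about 1.07 to 1.19 for shifts of 5 to 15% of patients, and the long-CPB odds ratio 1.00 to 1.13. That is modest beside an interaction test that could detect only a ratio of about 8.7.

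A reader might infer that the main result is at risk. It is not: CPB duration enters neither the crude nor the adjusted Cox model, and the sample size does not depend on it. One of six subgroup factors is affected. The correction is still worth making before the data are seen, because it costs little and stops a possibly biased row being read as randomised evidence.

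**What to change.** 1. In section 3.3.3, do one of the following.
   - Replace CPB duration with a factor known before randomisation, for example the planned procedure or the Cleveland Clinic risk stratum already used for randomisation.
   - Keep it, labelled as post-randomisation and exploratory, and report it outside the baseline-subgroup forest plot. Compare CPB duration between arms alongside it. A null comparison in a trial of this size would reassure but not prove that duration is unaffected.
2. In section 3.3.2.3, move the intraoperative items (CPB time, cross-clamp time, minimum temperature, transfusion, urine output, vasoactive drugs) to a separate list of intraoperative data, outside the pre-randomisation rule.
3. Define surgical type, both as a covariate in the adjusted Cox model and as a subgroup factor, by the planned procedure recorded before randomisation. Section 3.3.2.3 groups it with the intraoperative items and does not say whether planned or performed surgery is meant.

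Cost: wording in the analysis plan and the data collection form, one added between-arm comparison if the factor is kept, and one exploratory subgroup replaced or downgraded. Sample size, endpoint and primary test do not change.

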3.1 Study Design

This study is a randomized controlled, intervention-based clinical trial. Eligible patients were randomly assigned in a 1:1 ratio to either the ta-VNS group or the sham stimulation group. The primary endpoint was the incidence of acute kidney injury (AKI) within 7 days postoperatively. The objective of this study was to evaluate the efficacy and safety of continuous 6-day perioperative ta-VNS intervention in reducing the incidence of AKI following cardiac surgery under cardiopulmonary bypass (CPB).

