Unless otherwise specified, all tests were conducted as two-tailed tests with a significance level set at $\alpha = 0.05$, meaning that differences were considered statistically significant when $P < 0.05$.

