3.4 Research Flowchart

IV. Sample Size Calculation

The sample size for this study was estimated based on preliminary experimental results from our research center. In the pilot study, the incidence rates of CPB-associated AKI in the ta-VNS group and sham stimulation group were 17.1% and 37.9%, respectively. With a significance level of $\alpha = 0.05$ (bilateral) and a power of $1 - \beta = 0.80$, calculated using G*Power software (version 3.1.9.7), 68 patients were required in each group. Considering a 10% dropout rate, a total of 152 patients were enrolled in this study, with 76 patients in each group.

V. Data Management and Confidentiality

Only investigators authorized by the principal investigator are permitted to access or analyze data. Computer systems used for data management must be password-protected, and paper documentation must be locked.

All information related to the subject's identity is kept confidential, and such information shall not be disclosed beyond the scope permitted by applicable laws and/or regulations.

VI. Informed Consent

Prior to enrollment in this study, the investigator responsible for obtaining informed consent must provide each participant with a comprehensive written explanation regarding the study's objectives, nature, procedures, potential benefits, and risks. Participants should be informed of their right to withdraw from the study at any time. Before enrollment, each participant must be fully informed and given sufficient time to consider participation. Enrollment is permitted only after voluntary participation and signing of the informed consent form.

The vulnerable groups potentially involved in this study include elderly individuals and illiterate persons. If the subject is unable to read or sign the informed consent form due to lack of capacity for action, their guardian must act as proxy for the informed consent process and sign the document. If the subject lacks the ability to read the informed consent form (e.g., illiteracy), a witness must observe the informed consent process and sign the consent form.

VII. Adverse Events and Related Management Measures

ta-VNS is a selective, non-invasive, and low-risk effective VNS strategy. The primary

adverse events include pain, influenza-like symptoms, and local skin discomfort, which resolve immediately after cessation of stimulation. To date, no literature has reported serious adverse events associated with this procedure.

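### Adverse events are to be compared only by a χ²/Fisher P value; at 76 per arm a non-significant result cannot support a safety statement, so plan risk differences with 95% confidence intervals

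*Combined protocol and SAP*

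**What the plan says.** Section 3.1 gives the purpose of the trial as "to evaluate the efficacy and safety of continuous 6-day perioperative ta-VNS intervention".

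The AE and SAE analysis is two sentences in Section 3.3.3. The population comes first: "Safety analysis was based on the safety dataset (all subjects who received at least one stimulation". Then the comparison: "The incidence rates of all adverse events and serious adverse events were compared between groups using the" χ² test or Fisher's exact method. The decision rule closes the same section: "all tests were conducted as two-tailed tests with a significance level set at" 0.05, and "differences were considered statistically significant when" P is below 0.05. No risk difference, risk ratio or confidence interval is named for AEs or SAEs.

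Elsewhere Section 3.3.3 does name intervals. A 95% confidence interval is required for the hazard ratio of the primary outcome, the odds ratio for AKI severity and each subgroup odds ratio. New-onset atrial fibrillation, pulmonary infection, stroke and 30-day death are compared by χ² or Fisher, with a hazard ratio and 95% interval as an option if there are enough events.

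Section IV bases the sample size on AKI only, where pilot rates in the "ta-VNS group and sham stimulation group were 17.1% and 37.9%, respectively". It gives 68 per group, raised to 76 for 10% dropout.

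**The concern.** A test in a trial sized for another outcome can return a non-significant result for two different reasons: there is no excess of harm, or the trial is too small to see one. A P value does not separate the two; an interval does, because its upper limit shows how large an excess remains compatible with the data.

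As written, the plan gives the investigators no prespecified quantity on which to rest a statement about AEs and SAEs other than whether P falls below 0.05. The device is used off-label (Section 3.3.1), through surgery and for five days afterwards, and safety is a stated purpose. The report should be able to say what size of harm was excluded.

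**Working it through.** **Inputs.** From the documents: 1:1 allocation (3.1); 76 per group after dropout (IV); two-sided 0.05 and χ², with Fisher if expected frequencies are inadequate (3.3.3). Assumed: the AE/SAE rates, which the documents do not give; that all 76 per arm enter the safety set; and that Fisher replaces χ² when an expected count is below 5, since the plan gives no cut-off.

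**The plan's own figure.** With unpooled variance, n = (1.960 + 0.842)² × [p₁(1 − p₁) + p₂(1 − p₂)] / (p₁ − p₂)². For 0.379 and 0.171: 7.849 × (0.2354 + 0.1418) / 0.208² = 68.4, consistent with the stated 68. Then 68 / 0.90 = 75.6, so 76. The number is reproduced, and nothing in it concerns safety.

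**Power for a safety difference.** The normal approximation is Φ[(d − 1.96·s₀)/s₁], where d is the risk difference, s₀ = √[2p̄(1 − p̄)/n] and s₁ = √{[p₁(1 − p₁) + p₂(1 − p₂)]/n}. For 10% vs 20% at n = 76: s₀ = 0.0579, s₁ = 0.0574, and (0.10 − 0.1135)/0.0574 = −0.236, giving 41%. The table uses exact enumeration of all outcomes under two binomials.

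| Assumed sham vs ta-VNS | χ² | Fisher | Plan's rule (χ², Fisher if expected < 5) |
|---|---|---|---|
| 5% vs 10% | 22% | 13% | 20% |
| 10% vs 20% | 42% | 33% | 42% |
| 15% vs 30% | 61% | 54% | 61% |
| 20% vs 40% | 78% | 72% | 78% |
| 25% vs 50% | 90% | 87% | 90% |
| 5% vs 15% | 56% | 45% | 56% |
| 20% vs 30% | 30% | 24% | 30% |
| 30% vs 40% | 26% | 21% | 26% |
| 40% vs 50% | 23% | 19% | 23% |

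Two patterns follow.

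- *Doubling.* Power passes 50% at a sham rate of about 12% (χ²) or 14% (Fisher), and 80% at about 21% or 22.5%. With 68 per arm the 50% points are about 13% and 15%.
- *Fixed 10-point excess.* Power falls as the sham rate rises: 42% at 10%, 30% at 20%, 26% at 30%, 23% at 40%. At a sham rate of 5% it is 56% under the plan's rule, so the more-than-half statement starts at 10%.

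**What an interval would show.** Take 8/76 SAEs on ta-VNS and 4/76 on sham. The Wilson limits are 5.4% to 19.4% and 2.1% to 12.8%. The risk difference is 10.53 − 5.26 = +5.3 points. Newcombe limits:

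- lower: 5.26 − √[(10.53 − 5.43)² + (12.77 − 5.26)²] = −3.8 points
- upper: 5.26 + √[(19.42 − 10.53)² + (5.26 − 2.07)²] = +14.7 points

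Fisher P is 0.37 and χ² P is 0.23, so either test is non-significant while an excess of 14 points remains possible. At 16/76 vs 8/76, χ² P = 0.075 with an interval of −1.2 to +22.1. At 8/76 in each arm, the interval is −10.2 to +10.2.

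**The case against.** The strongest reply is that low power for safety is usual in a trial sized on efficacy, and that the plan is less bare than it may look. Categorical variables are to be shown as frequencies and percentages, so per-arm counts will be available and a reader could derive an interval. Section 3.3.3 also provides a conditional hazard ratio with a 95% interval for named 30-day outcomes. Section II, the formal objective, states efficacy only. All of this is correct and limits the point to AEs and SAEs. It does not remove it: the 30-day interval is optional, depends on event numbers and does not cover AEs or SAEs as such, and an interval that a reader can derive is not a prespecified basis for the conclusion.

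Three stronger readings are tempting, and the documents do not support them.

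- *A doubling of SAEs would be missed most of the time.* This depends on a sham rate that the documents do not give. It holds below about 12% to 14%. At 20% vs 40% power is 78% by χ². After bypass surgery, with SAEs counted from all causes, a higher rate cannot be excluded.
- *The miss rate for 5% vs 10% is 87%.* That comes from applying Fisher throughout. Under the plan's rule it is about 80%.
- *A non-significant result would be declared safe.* No section says so. The plan defines only when a difference is significant.

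**Conclusion.** The point holds in this form. For AEs and SAEs the plan names a significance test and no estimate or interval, in a trial sized on AKI alone. At 76 per arm, a 10-point excess is missed more than half the time at every sham rate checked from 10% to 40%, with power of about 23% to 42%. The conclusion that P > 0.05 cannot support a safety statement therefore does not hang on one assumed rate, although each power figure does. How often a doubling is missed does depend on the sham rate.

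This is a worthwhile, inexpensive improvement to the analysis plan. It does not affect the primary efficacy conclusion, and it does not show that the intervention is harmful.

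**What to change.** Amend the safety paragraph of Section 3.3.3 as follows.

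1. For all AEs, all SAEs, and the events that lead to discontinuation of stimulation (as the protocol already describes them in Sections 3.2.3 and 3.3.1), report per-arm counts and the risk difference, ta-VNS minus sham, with a two-sided 95% Newcombe or Miettinen-Nurminen interval.
2. Base the safety statement on the interval and quote its observed upper limit. No margin needs to be invented.
3. State that P > 0.05 will not be taken as evidence of safety. The χ²/Fisher P values may stay as descriptive.
4. Make clear that sham participants belong to the safety set. Membership requires at least one stimulation, while Section 3.3.1 has the sham output switched off.

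The cost is a few sentences and one table column, with no extra patients or data. It adds no power: the intervals will be wide (±10.2 points even with 8 events in each arm), so the safety statement will be less favourable than a bare non-significant P value might suggest.
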